1 PROTOCOL SUMMARY

1.1 SYNOPSIS

Title:

Intermittent Hypoxia and Caffeine in Infants Born Preterm (ICAF)

Study Description:

Our proposal will address the critical question: is persisting intermittent hypoxia (**IH**) in preterm infants associated with biochemical, structural, or functional injury, and is this injury attenuated with extended caffeine treatment? We will study the effects of caffeine on **IH** in 220 preterm infants born at ≤ 30 weeks + 6 days gestation. Infants who are currently being treated with routine caffeine, and who meet eligibility criteria, will be enrolled between 32 weeks + 0 days and 36 weeks + 6 days PMA. At enrollment, infants will be started on continuous pulse oximeter recording of O₂ saturation and heart rate. If, based on standard clinical criteria, the last dose of routine caffeine is given on or before the day the infant is 36 weeks + 5 days PMA, then, ideally, on the day following, but no later than the third calendar day following, their last dose of routine caffeine treatment, infants will be randomized (110/group) to extended caffeine treatment or placebo. Randomized infants should begin receiving study drug (i.e. 5 mg/kg/of caffeine base, or equal volume of placebo) on the day of randomization, but no later than the third calendar day following the last dose of routine caffeine. Prior to 36 weeks + 0 days PMA, study drug will be given once daily (i.e. 5mg/kg/day) and beginning at 36 weeks + 0 days PMA, study drug will be given twice daily (i.e. 10 mg/kg/day). The last dose of study drug will be given at 42 weeks + 6 days PMA. **Pulse oximeter**

recordings will continue either until hospital discharge or for 1 week after discontinuing study drug depending on whether the infant was recruited at a study site at which home oximetry recording is being performed. Two caffeine levels will be obtained, the 1st at one week after beginning study drug, but no later than 14 days post-first-dose of study drug. The 2nd targeted at 40 weeks + 0 days PMA, but no earlier than 39 weeks+ 0 days and no later than the last day of study drug, whether in hospital or at home. Inflammatory biomarkers will be measured at study enrollment and again at 38 weeks + 0 days PMA plus or minus 3 days, or within 2 calendar days prior to hospital discharge, whichever comes first. At study sites recruiting into the MRI part of the study, quantitative MRI/MRS should be obtained between study enrollment and 3 calendar days after starting study drug and again at a target date of 43 weeks + 0 days, but no later than 46 weeks + 6 days PMA.

Objectives:

Primary Objective 1: Compare the extent of **IH** exposure, from randomization through 42 weeks + 6 days PMA (within each gestational week and overall), in infants randomized to extended caffeine treatment to infants assigned to receive placebo.

Primary Objective 2: Compare changes in a panel of inflammation-related cytokines and chemokines, from enrollment to the target age of 38 weeks + 0 days PMA, in infants randomized to extended caffeine treatment to infants assigned to receive placebo.

Primary Objective 3: Compare changes in quantitative MRI structural, microstructural and metabolic biomarkers of acute injury, from enrollment to 43-46 weeks PMA, in infants randomized to extended caffeine treatment to infants assigned to receive placebo.

Secondary Objective 1: Examine the association between salivary caffeine concentrations and **IH** outcomes at the one week post randomization and 40 weeks + 0 days PMA assessments.

Secondary Objective 2: Determine whether caffeine effects on changes in inflammatory or MRI biomarkers from baseline to follow-up are mediated by caffeine-related reduced **IH**.

Endpoints:	
Primary:
 
 • Extent of IH as measured by seconds below 90% saturation per 24 hours of recorded oximetry data within each week PMA, and overall • Plasma concentration changes in inflammatory biomarkers between baseline and 38 weeks + 0 days PMA • MRI changes in microstructural measures between baseline and end of study (between 43 weeks + 0 days and 46 weeks + 6 days PMA). 
Secondary
 
 • #IH events per 24 hours of recorded oximetry data, # sec < 80% saturation per 24 hours of recorded oximetry data, nadir saturation during events, and the duration of events and area under of curve during events below 90% and 80% threshold saturation • Changes in inflammatory biomarkers and MRI measures of regional tissue volume between baseline and end of study in relation to IH measures
Study Population:	
Sample size: 220 infants, 110 caffeine and 110 placebo-treated
 
Gender: Male and female
 
Age: Enrollment at PMA 32 weeks + 0 days - 36 weeks + 6 days
 
Demographic Group: Infants born at \leq30 weeks + 6 days gestation
 
General Health Status: Clinically stable, on caffeine treatment and expected to receive last dose of routine caffeine treatment no later than 36 weeks + 5 days PMA
 
Geographic location: NICU or step down unit at a participating hospital, with final weeks at home following NICU discharge

Phase:	Not applicable
Description of Sites/Facilities Enrolling Participants:	Neonatal Intensive Care Units (NICU) in hospitals in metropolitan areas in the U.S. While inpatient the research will take place in the hospital. Once discharged, if the subject has been enrolled at a site performing MRIs, the patient will return to specified outpatient locations for performance of the follow-up MRI. At the end of the study, study termination procedures will be performed in a manner convenient for the family, and may be performed in person or remotely, and if applicable may be performed at the time of an MRI.
Description of Study Intervention:	Enrolled infants will be randomized to receive caffeine or equal volume placebo. The caffeine base dose will be 5 mg/kg once daily when the infant is at age 35 weeks + 6 days PMA or less. When the infant is at 36 weeks + 0 days PMA or more the caffeine base dose will be 5 mg/kg twice daily, based on the expected increased rate of caffeine metabolism that occurs as infants age.
Study Duration:	Enrollment is scheduled to start in December, 2018 and will continue at least through May of 2022, with completion of follow-up and data analyses thereafter.

Participant Duration: The maximum time between study enrollment to study completion for an individual participant would be 15 weeks if enrollment was as early as 32 weeks + 0 days and the final visit was at the latest time permitted at 46 weeks + 6 days. Since enrollment is permitted as late as 36 weeks + 6 days, and the final study visit may occur as early as 43 weeks + 6 days, a participant may complete the full study in as few as 7 weeks.

[figure not shown]
Hospital discharge most commonly occurs between 34 and 40 weeks PMA, and we expect most infants to have roughly half their time in the study as in-patient and half as outpatient, though this may be vary widely.

The end of study procedures include: return of the oximeter (if applicable), salivary sample and any unused study drug. As noted above, these procedures will be done at the convenience of the family, and although a face-to-visit is preferred, all items may be shipped back if, for any reason, the parents prefer not to travel to the site.

1.2 STUDY SCHEMA

Our goal is to randomize 220 infants born at a gestational age of 30 weeks + 6 days or less, who get their last dose of routine caffeine treatment between 32 weeks + 0 days and 36 weeks + 5 days PMA, to receive either extended caffeine treatment or placebo to 42 weeks + 6 days. As illustrated below, all NICU admissions of infants born at 30 weeks + 6 days or less will be noted in the screening log. Formal screening for eligibility will begin at 32 weeks + 0 days, with enrollment once infants meet all eligibility requirements, and the infant is at 36 weeks + 6 days or less PMA. Between enrollment and randomization, baseline data will be collected. Randomization will be performed, ideally, on the day following, but no later than the third calendar day following, the last dose of routine caffeine, as long as randomization and dosing is by 36 weeks + 6 days PMA. Outcome measures will include oxygen saturation recordings, plasma biomarkers and brain MRI.

FLOW DIAGRAM - ICAF

1.3 SCHEDULE OF ACTIVITIES (SOA)

Study Procedures	≤30 weeks + 6 days thru 36 weeks + 6 days	32 weeks + 0 days thru 36 weeks + 6 days	Target: 1 day post last routine caffeine dose (but window of up to 3 calendar days allowed)	1 week on study drug (up to 14 days post 1 st dose)	36 weeks + 0 days PMA	Hospital Discharge	40 weeks + 0 days PMA	42 weeks + 6 days PMA	43 weeks + 6 Days PMA
Screening	X								
Informed Consent		X							
Enrollment		X							
Baseline Data Collection		X							
Pulse oximetry recording						X ¹⁰			
Randomization			X						
Once daily study drug				X ¹					
Twice daily study drug							X ¹		
Drug log						X			
Saliva for caffeine level				X			X ²		
Biomarker blood sample		X ³				X ³			
MRI/MRS		X ⁴							X ⁴
Pre-discharge checklist						X ⁵			
Weekly parent phone contact							X ⁶		
Infant sleep Q								X ⁷	
End of study visit									X ⁸
Concomitant medications					X ⁹				
Adverse Event					X ⁹				

1. Study drug (caffeine base 5 mg/kg QD or placebo, weight adjusted weekly while in hospital) begins 1 day after last day of routine caffeine, but no later than the 3rd calendar day after last dose of routine caffeine. Dose is increased to 5 mg/kg BID at 36 + 0; finally, the last dose of study drug is at 42 + 6. Note that initial dose will be BID if enrolled at 36 + 0 or later.
2. 2nd caffeine level targeted at 40 + 0, (no earlier than 39 + 0 and no later than last day of study drug), whether in hospital or at home.
3. 1st biomarker blood sample should be obtained as close as possible to the day of randomization. Whenever possible, this blood sample should be timed with a clinically required blood draw. To facilitate obtaining this sample at the time of a clinical blood draw, this sample may be obtained at any time after consent, but no later than the 2nd calendar day after the first dose of study drug. The 2nd sample is to be obtained at 38 + 0 (+ or - 3 days) or within 2 calendar days prior to hospital discharge, whichever comes first.
4. 1st MRI/MRS is done in hospital sometime between enrollment and 3 calendar days after starting study drug. 2nd MRI/MRS is targeted at 43 + 0 but should be no later than 46 + 6. MRI visit may be combined with the end of study visit. MRI/MRS scans will only be performed for subjects enrolled at sites participating in the MRI/MRS portion of the study.
5. Includes documentation of tracking information, and parent training including: use of oximeter, drug administration, use of drug administration log, salivary sample collection, communication expectations and follow-up plans.
6. Weekly phone calls from study staff to parent(s) begin 1- 3 days after hospital discharge and continue through end of study follow up visit. A phone follow-up form will be completed to collect clinical data, adverse events, and document family questions.
7. Sleep Assessment (BISQ) done over the phone with parent at 42 weeks.
8. The end of study visit, which may be done remotely, is targeted for 43 + 6 days, or one week after the last dose of study drug, whichever comes first, but should be completed no later than 46 + 6. Study staff will collect the study drug log, used bottles, unused drug, study oximeter, and frozen salivary sample. Items may be shipped back if the parents opt for a remote visit.
9. Collection of concomitant medications and adverse event monitoring and reporting are continuous throughout study.
10. Home-oximetry will only be performed for subjects enrolled at sites participating in the home-oximetry portion of the study.

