8.1.2 INFLAMMATORY BIOMARKERS

An EDTA blood sample (0.6 – 0.8 ml) to measure a panel of inflammatory biomarkers will be obtained at enrollment prior to randomization, and again at 38 weeks + 0 days PMA or NICU discharge, whichever comes first. The blood will be centrifuged and the resultant plasma aliquoted into tubes and immediately frozen (-80 °C). The intent is to freeze a plasma volume of at least 0.3 ml. As specified by later shipping instructions, the frozen samples will be batched and shipped on dry ice overnight using shipping labels that will be provided.

Bulk analyses of inflammatory biomarker plasma concentrations will be performed at Children's National Medical Center using a commercially available ELISA multi-spot assay to measure inflammation-related proteins from different functional categories of cytokines and chemokines, including growth factors, and adhesion molecules, IFN-alpha, IL-6, Gro/CXCL1, IL-1 β , IL-4-6, IL-6 receptor, IL-8, IL-10, IL-13, ICAM-1, myeloperoxidase, CRP, MCP, IGFBP-1, MIP-1a, RANTES, and TNFa. Analytes that show strong trends or significance with this assay may be further analyzed with individual ELISA assays, to confirm the original result.

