Analyses for this objective will be performed on the mITT population and compare those randomized to extended caffeine vs. placebo. To be included in the analyses a subject must have had a baseline/follow-up pair of blood samples for which at least one biomarker was measured on both samples. Analysis will focus on change in inflammatory biomarker levels over the study period. Preliminary analyses will examine the distribution of biomarkers, and data will be transformed (e.g., logged) as appropriate for analysis. Two approaches will be taken for the primary analyses, comparing changes in biomarkers over the study period in extended caffeine vs. placebo infants. First, we will conduct separate analyses of each inflammatory biomarker using linear regression models to compare study groups at study completion, controlling for baseline levels as well as key covariates including morbidities that might be associated with inflammation, using the Benjamini and Hochberg method to account for multiple testing by controlling the false discovery rate. Second, we will examine the structure of the biomarker data using data reduction procedures of factor analyses (identifying latent variables reflected by the set of biomarkers) and latent profile analysis (identifying subgroups of infants with similar patterns of biomarker profiles). Extended caffeine vs. placebo infants would then be compared on the summary measures of inflammation biomarkers resulting from these analyses.

Primary Objective 3: Compare changes in quantitative MRI structural, microstructural and metabolic biomarkers of acute injury, from enrollment to 43-46 weeks PMA, in infants randomized to extended caffeine treatment to infants assigned to receive placebo.

Analyses for this objective will be performed on the mITT population and compare those randomized to extended caffeine vs. placebo. To be included in the analyses a subject must have had a baseline/follow-up pair of MRI studies completed from which at least one MRI endpoint could be measured on both assessments.

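### The first biomarker sample may be drawn up to two days after the first study dose, in conflict with section 8.1.2, and section 9.4.2 adjusts for it without requiring a pre-dose value

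*Combined protocol and SAP*

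**What the plan says.** **Timing of the first blood sample.** Footnote 3 of section 1.3 states a target, "1st biomarker blood sample should be obtained as close as possible to the day of randomization", and then an outer limit, "no later than the 2nd calendar day after the first dose of study drug", with any moment from consent onward allowed. The stated reason is to let the sample coincide with a clinical draw. Section 8.1.2 says the sample "will be obtained at enrollment prior to randomization, and again at 38 weeks + 0 days PMA or NICU discharge, whichever comes first". The synopsis (section 1.1) says "Inflammatory biomarkers will be measured at study enrollment and again at 38 weeks + 0 days PMA", and the schema (section 1.2) places baseline data collection between enrollment and randomization.

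**Analysis.** For Primary Objective 2, section 9.4.2 fits a linear regression to each biomarker at follow-up, "controlling for baseline levels as well as key covariates". Entry requires a baseline/follow-up pair with at least one biomarker measured on both samples. Nothing requires the first sample to precede dosing, and samples taken after dosing are not flagged or analyzed separately.

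**MRI.** Footnote 4 of section 1.3 places the first scan "sometime between enrollment and 3 calendar days after starting study drug". Section 1.1 gives the same window. The MRI model in section 9.4.2 also controls for the baseline parameter.

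**The concern.** A site that follows footnote 3 can depart from section 8.1.2, so the protocol gives two rules for one sample.

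The statistical consequence is adjustment for a post-treatment covariate. Section 9.1 hypothesizes that caffeine lowers the same analytes that enter the model as baseline. If a first sample is taken once the arms have begun to diverge, part of the treatment difference sits in the covariate, and the adjusted comparison subtracts a fraction of it. For those infants the first value no longer describes the state before treatment, although the objective is change from enrollment. Two of the three primary objectives use this form of adjustment.

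**Working it through.** **Plan's own figures.** Section 9.2 gives one power figure, 82%, for the intermittent hypoxia outcome (100 per group, effect 0.50 SD). A normal-approximation check with alpha 0.05/7, reading 36 to 42 weeks as seven tests, gives 80.1%. This does not bear on the present point. No effect size or power is given for the biomarkers.

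**Step 1: bias formula.** Let D be the true difference between arms at follow-up, E the difference already present when a post-dose first sample is drawn, f the share of infants sampled post-dose, and b the within-arm slope of follow-up on baseline. Then

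adjusted estimate ≈ D − b × f × E.

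Writing e = E/D, the proportion lost is b × f × e. A simulation with b = 0.5, f = 1, e = 0.5 and D = 0.50 SD gave 0.376, against 0.50 × (1 − 0.25) = 0.375 expected.

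**Step 2: inputs.** The documents give none of b, f or e. The assumed ranges are b 0.3 to 0.7, f 0.25 to 1.0 and e 0.1 to 0.5.

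| Case | b | f | e | Proportion lost |
|---|---|---|---|---|
| Low | 0.3 | 0.25 | 0.1 | 0.75% |
| Middle | 0.5 | 0.5 | 0.25 | 6.25% |
| High, half sampled late | 0.7 | 0.5 | 0.5 | 17.5% |
| Extreme, all sampled late | 0.7 | 1.0 | 0.5 | 35% |

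**Step 3: direction.** If E and D have the same sign, the estimate shrinks. If e is negative, it grows: the middle case with e = −0.25 gives 0.50 × (1 + 0.0625) = 0.531 SD. If E is not zero but D is zero, a difference of −b × f × E appears. If E and D are both zero, the type I error is unaffected.

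**Step 4: illustrative power.** Assume 100 per group, D = 0.50 SD (both borrowed from Objective 1), b = 0.5 and residual SD √(1 − 0.25) = 0.866. The strictest Benjamini-Hochberg step is taken as 0.05/17, counting 17 listed analytes.

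| f, e | Estimate (SD) | Power at 0.05 | Power at 0.05/17 |
|---|---|---|---|
| All samples pre-dose | 0.500 | 98.3% | 86.6% |
| 0.5, 0.1 | 0.487 | 97.8% | 84.3% |
| 0.5, 0.25 | 0.469 | 96.9% | 80.3% |
| 1.0, 0.5 | 0.375 | 86.5% | 53.5% |

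**Step 5: where e is likely to lie.** Section 2.1 says routine caffeine most commonly stops at 33 to 35 weeks, which is 21 to 35 days before 38 weeks + 0 days. If the effect built up linearly (an assumption), two days would carry 2/35 = 5.7% to 2/21 = 9.5% of it. With b 0.3 to 0.7 and f 0.25 to 0.5, the loss is 0.3 × 0.25 × 0.057 = 0.4% to 0.7 × 0.5 × 0.095 = 3.3%.

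Some infants have a larger share. With a first dose at 36 + 6, the first sample may be at 37 + 1 and the second as early as 37 + 4, five days after the first dose. Then e = 2/5 = 40% under the same assumption. Early discharge can also shorten the interval.

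**Step 6: MRI.** From a first dose at 36 + 6 or 32 + 0 to a scan at 43 + 0 is 43 or 77 days. Three days is 3/77 = 3.9% to 3/43 = 7.0%, probably a smaller early share than for blood.

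**The case against.** The strongest defense is that the window is short and has a purpose. Footnote 3 aims at the day of randomization and exists so that clinical draws can be used, and the risk assessment in sections 2.2.1 and 2.2.3 relies on that. All infants have recently been on caffeine, and section 6.1.2 notes its relatively long half-life, so the arms may barely differ after two days. Section 3 treats the interval to 38 weeks as the time needed for biomarker change, which also suggests little early effect. This stands as an argument that the bias is probably small. It does not remove the conflict between sections, and it does not supply an analysis rule.

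A reader might infer that placebo infants have been off caffeine for several days at baseline while the other arm has not. The first dose may come on the third calendar day after the last routine dose and the sample two days later, so five calendar days off caffeine is possible on placebo. But both arms share the gap before the first study dose. They can differ only from that dose on: at most 2 calendar days for blood and 3 for MRI.

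A reader might also infer that the MRI window contradicts another section. It does not: sections 1.1 and 1.3 agree. Only the adjustment issue carries over.

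**Conclusion.** The conflict between footnote 3 and sections 1.1, 1.2 and 8.1.2 is in current text and must be reconciled. The analysis issue is also real: as written, section 9.4.2 can adjust a primary comparison for a value taken after dosing. It affects only infants sampled after their first dose.

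The size is unknown. Under assumed inputs it runs from under 1% to about 18% of the effect, with 35% only if every infant is sampled late, half the effect is already present and the slope is 0.7. For most infants the low end is more likely. The exceptions are infants randomized late or discharged early.

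Two stronger readings are not supported. One is that the bias always runs toward no effect; that needs an early effect in the same direction as the final one, and the documents give no sign for a two-day effect. The other is that any percentage here is an estimate for this trial; each depends on assumed values of b, f and e. The point is worth correcting because the remedy is cheap and the result need not then rest on an untested assumption about early response.

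**What to change.** 1. Reconcile sections 1.1, 1.2, 1.3 (footnote 3) and 8.1.2 so that they state one rule for the first sample.
2. In section 9.4.2, for Primary Objectives 2 and 3, define baseline as the last sample or scan before the first study dose. Apply this from recorded times of the sample or scan and of the first dose; dates alone cannot order events on the dosing day.
3. For infants with only a post-dose first value, relax the pair rule, keep the follow-up value, treat baseline as missing and impute it from pre-randomization covariates. Section 9.4.1 already foresees multiple imputation for missing data in sensitivity analyses.
4. Use post-dose values as baseline only in a prespecified sensitivity analysis, and report how many infants have them.

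With every baseline used in the model pre-dose, or imputed from pre-randomization data, f is 0 and this bias disappears.

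**Cost.** Wording changes, and slightly less precision for infants without a measured pre-dose value. If the collection window is kept so that clinical draws can be used, no extra blood draw is needed. Tightening the window itself is different: some infants might need a research-only draw or lose a measured baseline, since inclusion criterion 2 (section 5.1) admits infants through the third calendar day after routine caffeine, which can be the last permitted dosing day.
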